1.1 Background

Unmet Medical Need

Idiopathic pulmonary fibrosis (IPF) is a chronic, progressive, fibrotic interstitial lung disease, associated with a median survival of 2-5 years from initial diagnosis [Raghu et al 2011](#). IPF affects approximately 1.5 million patients worldwide. Recently, nintedanib and pirfenidone were shown to slow the rate of IPF progression by targeting the biology of fibroblasts [King et al 2014](#), [Richeldi et al 2014](#). However, it was shown that nintedanib and pirfenidone cannot halt the progression of IPF disease. Furthermore, neither nintedanib nor pirfenidone was able to demonstrate a significant impact on IPF mortality. Therefore, a considerable unmet medical need remains.

Rationale for targeting B cells in IPF

There is supporting evidence to suggest that host immune response plays a pivotal role in the pathogenesis of IPF. Immunofluorescent patterns in IPF lung tissue demonstrate the presence of immunoglobulins within the alveolar walls of IPF specimens [Schwarz et al 1978](#). Immune complexes are present in alveolar fluid obtained from patients with IPF [Dall'Aglio et al 1988](#). Transcript analysis demonstrates an increase in expression of immunoglobulin genes in IPF [Zuo et al 2002](#). Tertiary lymphoid tissue (germinal centers and lymphoid aggregates) is present in lung tissue obtained from patients with IPF [Marchal-Sommé et al 2006](#). Radiographic imaging demonstrates the presence of mediastinal and hilar lymphadenopathy in up to 58% of IPF patients [Hunninghake et al 2003](#), [Attili et al 2006](#). Circulating autoantibodies and pulmonary immune complex deposits are seen in a majority of IPF patients [Magro et al 2003](#), [Magro et al 2006](#), [Grigolo et al 1998](#), [Fujita et al 1999](#), [Dobashi et al 2000](#), [Ogushi et al 2001](#), [Yang et al 2002](#), [Fischer et al 2006](#), [Takahashi et al 2007](#), [Kurosu et al 2008](#), [Taillé et al 2011](#). In addition, the presence of autoimmune antibodies in IPF confers a poor prognosis [Kahloon et al 2013](#).

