11.5 Analysis of secondary variable(s)

11.5.1 Efficacy / Pharmacodynamics

Survival analysis

At the end of the treatment epoch, the Kaplan-Meier estimates of the proportion of patients with the event of interest, along with 80% two-sided confidence intervals using Greenwood's formula, will be provided. In addition, the Kaplan-Meier estimates will be plotted against time.

The two treatment groups will be compared using a one-sided logrank test at the 10% significance level. The hazard ratio and its associated 80% two-sided confidence intervals will be estimated.

Event of interest is defined as:

1. All-cause mortality
2. IPF-related mortality

Progression-free survival (PFS) analysis

Same survival analysis as defined above will be produced at the end of the treatment epoch for the following event of interest:

1. Events, defined as: death (all-cause mortality) **OR** "progression" (relative reduction in FVC $\geq 10\%$)
2. Events, defined as: death (IPF-related mortality) **OR** "progression" (relative reduction in FVC $\geq 10\%$)

Disease progression

At the end of the treatment epoch, the Kaplan-Meier estimates of the proportion of patients with progression, along with 80% two-sided confidence intervals using Greenwood's formula, will be provided. The two treatment groups will be compared using a one-sided logrank test at the 10% significance level. The hazard ratio and its associated 80% two-sided confidence intervals will be estimated.

1. Progression, defined as: relative reduction in FVC $\geq 10\%$
2. Progression, defined as: relative reduction in DLcO $\geq 15\%$
3. Progression, defined as: absolute reduction in 6MWD ≥ 50 m

Composite endpoint

At the end of the treatment epoch, the Kaplan-Meier estimates of the proportion of patients with event of interest, along with 80% two-sided confidence intervals using Greenwood's formula, will be provided, where events of interest is defined as below. The two treatment groups will be compared using a one-sided logrank test at the 10% significance level. The hazard ratio and its associated 80% two-sided confidence intervals will be estimated.

1. death (all-cause mortality), **OR** relative reduction in FVC $\geq 10\%$, **OR** relative reduction in DLcO $\geq 15\%$, **OR** relative reduction in 6MWD ≥ 50 m
2. death (IPF-related mortality), **OR** relative reduction in FVC $\geq 10\%$, **OR** relative reduction in DLcO $\geq 15\%$, **OR** relative reduction in 6MWD ≥ 50 m

Pulmonary physiology

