6.2 Secondary objectives

6.2.1 Variables

6.2.1.1 Survival (all-cause mortality and IPF-related mortality)

Only events restricted to treatment epoch will be analyzed.

Survival all-cause mortality (S1) is defined as time from randomization to death due to any cause.

Survival IPF related mortality (S2) is defined as time from randomization to death due to IPF related cause.

IPF-related death will be assessed by an Adjudication Committee.

Survival time will be derived in days as follows:

$$(\text{date of death or censoring date} - \text{date of randomization}) + 1$$

For S1, if a patient is not known to have died (all-cause mortality) at the end of the treatment epoch, survival time will be censored at the latest date in treatment epoch where the patient was known to be alive.

For S2, if a patient is not known to have died due to IPF related cause at the end of the treatment epoch, survival time will be censored at the latest date in treatment epoch where the patient was known to be alive or died due to non-IPF related cause.

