6.2.1.2 Progression-free Survival

Only events restricted to treatment epoch will be analyzed.

Progression free survival (PFS) is defined as follows:

- PFS1: time from randomization to progression (relative reduction in FVC $\geq 10\%$) or death due to all causes
- PFS2: time from randomization to progression (relative reduction in FVC $\geq 10\%$) or death due to IPF related causes

For PFS1, if a subject has not progressed nor died at the end of the treatment epoch, PFS will be censored at the date of last non-missing assessment of FVC

For PFS2, if a subject has not progressed nor died (IPF related mortality) at the end of the treatment epoch, PFS will be censored at the maximum date of (the last non-missing assessment of FVC during treatment epoch and the non-IPF related death).

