6.2.1.3 Disease Progression

Only events restricted to treatment epoch will be analyzed.

Disease progression is defined as the time from randomization to progression.

The following progression events will be considered:

- Progression, defined as: relative reduction in FVC $\geq 10\%$;

- Progression, defined as: relative reduction in DLCO $\geq 15\%$;
- Progression, defined as: absolute reduction in 6MWD ≥ 50 m.

For the subjects who have not progressed at the end of the treatment epoch, disease progression will be censored at the date of the last FVC, DLCO or 6MWD assessment in treatment epoch as applicable.

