6.2.3 Statistical model, assumptions and hypotheses

6.2.3.1 Time to Events analyses

CCI

The Kaplan-Meier estimates of the proportion of patients with the event of interest in each treatment group, along with 80 % two-sided confidence intervals using Greenwood's formula, will be provided. The two treatment groups will be compared using a one-sided log rank test at the 10% significance level. The hazard ratio and its associated 80% two-sided confidence interval will be estimated based on a Cox regression model using treatment group as main factor.

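### For six time-to-event summaries the Kaplan-Meier figure is presented as a proportion of patients although competing deaths are censored, so it modestly overstates the observed cumulative incidence

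*SAP*

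**What the plan says.** SAP 6.2.3.1 plans, for every time-to-event endpoint, "The Kaplan-Meier estimates of the proportion of patients with the event of interest in each treatment group", with 80% Greenwood intervals, a one-sided log-rank test at 10% and a Cox hazard ratio. Protocol 11.5.1 plans the same estimator; for disease progression its words are "the Kaplan-Meier estimates of the proportion of patients with progression, along with 80% two-sided confidence intervals using Greenwood's formula, will be provided".

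The handling of death differs by endpoint:

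- **FVC, DLCO and 6MWD progression (SAP 6.2.1.3).** For patients without progression, "disease progression will be censored at the date of the last FVC, DLCO or 6MWD assessment in treatment epoch as applicable". Death is not mentioned, so any death without measured progression, whether IPF-related or not, is censored at the last test.
- **S2, IPF-related mortality (SAP 6.2.1.1).** Censoring is at "the latest date in treatment epoch where the patient was known to be alive or died due to non-IPF related cause".
- **PFS2 (SAP 6.2.1.2).** Censoring is at the later of "the last non-missing assessment of FVC during treatment epoch and the non-IPF related death".
- **Composite (b) (SAP 6.2.1.4).** Patients without an event are censored at their latest FVC, DLCO or 6MWD test. A non-IPF death is not an event, so it falls under this rule by default.
- **S1, PFS1 and composite (a).** Every death is an event, so the issue does not arise.

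The visible text of both documents names no cumulative incidence or other competing-risk estimator.

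**The concern.** A patient who has died cannot later show a 10% fall in FVC. Kaplan-Meier treats a censored patient as still exposed to the same future risk as those who remain under observation. With deaths censored, one minus Kaplan-Meier therefore estimates how many would progress if nobody died. It does not estimate what share of the randomised patients was observed to progress, which is how the documents describe it. The same applies to S2, PFS2 and composite (b), with non-IPF death as the competing event.

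At stake are six of the nine reported proportions and their curves. Such figures from an exploratory trial are read literally when a later study is planned. The excess depends on both the progression rate and the death rate in each arm, so it need not cancel in the between-arm difference.

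**Working it through.** **Inputs.** The documents give no event rate, death rate or power for these endpoints (protocol 11.8 says power for key secondary variables is not applicable), so there is no planned figure to reproduce. From the documents: 58 patients randomised 1:1, so 29 per arm (protocol 11.7); post-baseline efficacy visits at Weeks 13, 25, 37 and 49 (protocol 3.1); and one survival figure, "associated with a median survival of 2-5 years from initial diagnosis" (protocol 1.1). Assumed, as ranges:

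- progression q = 20-40% by one minus Kaplan-Meier at 48 weeks;
- death d = 2-10%, the 48-week probability of death acting alone on patients who have not progressed;
- non-IPF death of 1-5%.

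**Mortality implied by the protocol's survival figure.** With exponential survival and 48/52 = 0.923 years, 1 − 2^(−0.923/5) = 12.0% and 1 − 2^(−0.923/2) = 27.4%. These are all-cause rates from diagnosis, so they serve as an extreme.

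**Quarterly form.** Let h = 1 − (1−q)^(1/4) and g = 1 − (1−d)^(1/4), with deaths falling between visits. Then one minus Kaplan-Meier is q, and cumulative incidence = Σ (1−g)^k (1−h)^(k−1) h for k = 1 to 4. With q = 30% and d = 5%, h = 0.0853 and g = 0.0127; the cumulative incidence is 29.1%, an excess of 0.9 points. Excess of one minus Kaplan-Meier, in percentage points:

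| q | d = 2% | 5% | 10% | 12% | 27% |
|---|---|---|---|---|---|
| 20% | 0.2 | 0.6 | 1.2 | 1.5 | 3.5 |
| 30% | 0.4 | 0.9 | 1.8 | 2.2 | 5.1 |
| 40% | 0.5 | 1.2 | 2.4 | 2.9 | 6.7 |

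**Continuous form.** With λ1 = −ln(1−q) and λ2 = −ln(1−d), cumulative incidence = λ1/(λ1+λ2) × [1 − exp(−(λ1+λ2))]. The excess is 0.2-1.9 points over q = 20-40% and d = 2-10%, and 2.8-5.3 points at 27% mortality.

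**IPF-related endpoints (continuous form, non-IPF death 1-5%).** S2 with events in 3-20%: 0.02-0.5 points. PFS2 and composite (b) with events in 20-60%: 0.1-1.3 points.

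**Worked arm of 29.** One death before each of the first three visits, and 2, 2, 3 and 3 progressions at the four visits. Kaplan-Meier: 1 − (26/28)(23/25)(19/22)(16/19) = 37.9%. Observed: 10/29 = 34.5%, which is also the cumulative incidence here.

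**Simulation.** In 20,000 arms of 29 with quarterly visits and 30% progression, one minus Kaplan-Meier was never below the cumulative incidence. At 2%, 5% and 10% death it was strictly above in 39%, 71% and 92% of arms. The mean excess was 0.4, 0.9 and 1.8 points, and the 95th percentile 1.5, 2.7 and 4.5 points.

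**Between arms (continuous form).** Kaplan-Meier figures of 40% v 30% with deaths of 10% v 5% differ by 10.0 points; the cumulative incidences differ by 8.8. With 30% in both arms and deaths of 10% v 2%, the Kaplan-Meier difference is 0, while the cumulative incidences differ by 1.2 points.

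**Precision for comparison.** An approximate 80% half-width at 40% with 29 patients is 1.28 × √(0.4 × 0.6/29) = 11.7 points. One patient is 1/29 = 3.4 points.

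**The case against.** The case for leaving the plan alone has real force.

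- **Size.** An excess of 0.2-2.4 points is less than one patient per arm and at most about a fifth of the confidence half-width (2.4/11.7). This stands, and it limits the priority.
- **Non-IPF death.** Inclusion criterion 8 selects against it, so the IPF-related endpoints gain little. This stands; the case rests mainly on the three progression endpoints.
- **Existing summaries.** SAP 6.2.2 lists and summarises the events, and S1, PFS1 and composite (a) count all deaths. This helps in part. A crude proportion equals the cumulative incidence only without other loss to follow-up, and DLCO and 6MWD progression have no all-cause counterpart of their own.
- **Redaction.** A redaction mark opens SAP 6.2.3.1, so hidden text on the method cannot be excluded. The visible sentence nevertheless specifies Kaplan-Meier without qualification.

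A reader might also go further than the documents allow:

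- *The arm with more deaths always has the larger overstatement.* This holds only at equal progression rates. In the continuous form, 15% progression with 10% death gives 0.74 points, while 40% progression with 5% death gives 0.92.
- *The treatment comparisons are invalid.* They are not. Log-rank and Cox with this censoring are legitimate cause-specific comparisons.
- *An error of about 5 points should be expected.* That needs about 27% mortality, taken from a 2-year median measured from diagnosis. It is not measured from randomisation in a population selected on FVC, DLCO and absence of recent exacerbation, and it assumes that no death follows progression.
- *True progression is overstated.* The comparison is with observed progression. Decline between the last quarterly visit and death is unseen, so true progression may exceed both estimates.

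**Conclusion.** The point holds as a mismatch between the estimator and its description, for six of nine time-to-event summaries: the three progression endpoints, S2, PFS2 and composite (b). The direction is certain. One minus Kaplan-Meier is at or above the cumulative incidence of the observed event, and strictly above it once a competing death precedes a later event.

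The size is modest and rests on assumed rates: for progression, about 0.2-2.4 points at the assumed 2-10% death. Around 5 points (2.8-6.7, depending on the progression rate and visit pattern) arises only at the extreme 27% mortality. S2 is out by about 0.5 points or less, and PFS2 and composite (b) by 0.1-1.3 points.

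The documents do not support reading this as a flaw in the tests, the primary analysis or the sample size, or as a bias in a known direction between arms. Priority is low to moderate; the main reason to act is that the correction is cheap.

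**What to change.** In SAP 6.2.3.1, report the Aalen-Johansen cumulative incidence by arm with an 80% confidence interval, and plot it, for:

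- FVC, DLCO and 6MWD progression, with death from any cause as the competing event (the main gain);
- S2, PFS2 and composite (b), with non-IPF death as the competing event, for consistency.

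In SAP 6.2.1.1 to 6.2.1.4, enter the competing death on its own date instead of censoring at it or at the last assessment. Keep the log-rank test and the Cox hazard ratio for these six endpoints and label them cause-specific. Keep Kaplan-Meier for S1, PFS1 and composite (a).

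Protocol 11.5.1 prespecifies Kaplan-Meier with Greenwood intervals, so either amend it or record the estimator as a documented change from protocol; changing the SAP alone would put the two at odds.

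The cost is wording in both places and an event code in the time-to-event datasets. Survival analysis already needs death dates and adjudicated causes (SAP 6.2.1.1, protocol 10.5), so no new data and no change in sample size are required.

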6.2.1.4 Composite endpoint

Only events restricted to treatment epoch will be analyzed.

Time to composite events will be considered, where events of interest are defined as below:

- Death (all-cause mortality), OR relative reduction in FVC $\geq 10\%$, OR relative reduction in DLCO $\geq 15\%$, OR relative reduction in 6MWD ≥ 50 m;
- Death (IPF-related mortality), OR relative reduction in FVC $\geq 10\%$, OR relative reduction in DLCO $\geq 15\%$, OR relative reduction in 6MWD ≥ 50 m.

For the subjects who do not experience the events at the end of the treatment epoch, the time to event will be censored at the latest date of the FVC, DLCO or 6MWD assessments in the treatment epoch.

6.2.1.5 Pulmonary Physiology

Change from baseline in DLCO and in TLC during the treatment epoch

6.2.1.6 Exercise capacity

Change from baseline in 6-minute walking distance (6MWD), in distance-saturation product (DSP) and in post 6-minute walking test (6MWT) Borg dyspnea score during the treatment epoch.

Note: DSP = 6MWD * end of test oxygen saturation.

6.2.1.7 Gas Exchange

Change from baseline in resting oxygen saturation during treatment epoch

Commercially Confidential Information

6.2.2 Descriptive analyses

A list and a summary of the events (Survival, Progression-free Survival, Disease Progression and Composite Endpoint) within and outside the treatment epoch (as applicable) will be

provided. In the analyses on composite events a summary of the single events (the one occurring first) will be provided too.

Summary statistics of change from baseline by treatment and visit will be presented for DLCO and TLC, 6-minute walking distance, in distance-saturation product and in post 6MWT, resting oxygen saturation

Commercially Confidential Information

6.2.3 Statistical model, assumptions and hypotheses

6.2.3.1 Time to Events analyses

CCI

The Kaplan-Meier estimates of the proportion of patients with the event of interest in each treatment group, along with 80 % two-sided confidence intervals using Greenwood's formula, will be provided. The two treatment groups will be compared using a one-sided log rank test at the 10% significance level. The hazard ratio and its associated 80% two-sided confidence interval will be estimated based on a Cox regression model using treatment group as main factor.

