1.4 Study design and treatment

This is an exploratory (non-confirmatory) randomized, patient-, investigator-, sponsor blinded, and placebo controlled study of VAY736 in IPF patients. This study will investigate the safety and efficacy of VAY736 administered s.c. every 4 weeks for 48 weeks. Approximately 58 subjects will be randomized in a 1:1 ratio on top of local standard of care (SOC), to receive VAY736 or placebo. Randomization will be stratified by SoC medication (3 levels: nintedanib, pirfenidone, or no treatment). The randomization scheme will be performed separately within each stratum to ensure balance of the treatment groups with respect to the SoC medication.

A screening epoch of 6 weeks will be used to assess eligibility.

Randomized subjects will participate in a 48 week treatment epoch

Commercially Confidential Information

A scheme of the study design is provided in the figure below.

Figure 1-1 Study design

Commercially Confidential Information

2 First interpretable results (FIR)

First interpretable results (FIR) will be provided for this trial.

Commercially Confidential Information

The template shows the analysis / results to be presented in the FIR. Study outputs required to be created at the time of the FIR will be highlighted in TFL shells document and marked as “Key” in the Programming Deliverables Tracker (PDT) output list.

3 Interim analyses

Commercially Confidential Information

Commercially Confidential Information

Commercially Confidential Information

4 Statistical methods

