6.1.3 Statistical model, assumptions and hypotheses

The following hypothesis will be tested for VAY736+SoC versus Placebo+SoC:

H0: There is no difference or worsening in change from baseline in FVC (L) from baseline to 48 weeks of treatment between VAY736+SoC and placebo+SoC

H1: There is an improvement in change from baseline in FVC (L) from baseline to 48 weeks of treatment between VAY736+SoC and placebo+SoC

Test will be conducted at a one-sided 10% level and 2-sided 80% CI of the estimates will be displayed. Sense of the one-sided test for each criteria is given in table of appendix 1 (section 10.1).

The primary variable, change from baseline in FVC (L) will be analyzed using a Mixed Effects Model for Repeated Measures (MMRM) in the PD analysis set and considering all assessments collected during the treatment epoch. The model will include treatment and visit as fixed effects, standard of care treatment (Nintedanib, Pirofendone, or no treatment) as factor and baseline value as a covariate, treatment-by-visit and baseline-by-visit as interaction terms. The within subject correlation will be modeled using a repeated statement in SAS Proc Mixed with unstructured covariance matrix. In case of non convergence the model, an alternative AR(1) covariance may be implemented. The posterior will be derived as a t-distribution using a PROC MIXED as detailed in section 3. The main comparison will be a contrast between treatment groups at 48 weeks of treatment. This approach assumes data is Missing At Random (MAR).

Commercially Confidential Information

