6.2.3.2 Pulmonary Physiology, Exercise capacity, Gas Exchange

CCI

The same MMRM model described for the primary endpoint will be used in these analyses using SAS Proc Mixed.

Commercially Confidential Information

An ANCOVA

model will be fitted with treatment group as main factor, standard of care therapy (stratification factor) as a cofactor and baseline as covariate.

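### The time-to-event tests ignore the standard-of-care randomisation strata, and Kaplan-Meier overstates the percentage progressing because deaths are censored

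*SAP*

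**What the plan says.** **Strata.** SAP 1.4 sets the design: "Randomization will be stratified by SoC medication (3 levels: nintedanib, pirfenidone, or no treatment". The primary MMRM in SAP 6.1.3 includes "standard of care treatment (Nintedanib, Pirofendone, or no treatment) as factor and baseline value as a covariate". SAP 6.2.3.2 reuses that MMRM for the continuous secondary endpoints and gives an ANCOVA with "standard of care therapy (stratification factor) as a cofactor and baseline as covariate". The sensitivity ANCOVA in SAP Appendix 2 carries SoC as well.

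The time-to-event analyses do not. Protocol 11.5.1 says "The two treatment groups will be compared using a one-sided logrank test at the 10% significance level", and SAP 6.2.3.1 repeats this without strata. The hazard ratio is "estimated based on a Cox regression model using treatment group as main factor".

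**Reported percentage.** SAP 6.2.3.1 promises "The Kaplan-Meier estimates of the proportion of patients with the event of interest in each treatment group", and Protocol 11.5.1 uses the same idea for progression. Under SAP 6.2.1.3, for patients who have not progressed, "disease progression will be censored at the date of the last FVC, DLCO or 6MWD assessment in treatment epoch as applicable". There is no separate rule for death. For IPF-related mortality, SAP 6.2.1.1 censors at the "latest date in treatment epoch where the patient was known to be alive or died due to non-IPF related cause". SAP 6.2.1.2 and 6.2.1.4 likewise censor non-IPF deaths in PFS2 and in composite version (b).

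**The concern.** **Strata.** Analysing by the factor used to randomise is the usual match between design and analysis, and this SAP follows it everywhere readable except here. If SoC predicts progression, ignoring it makes the log-rank test somewhat conservative. The hazard ratio is then an average over strata, while the FVC effect is adjusted for them. Protocol 1.1 says both background drugs slow progression, so a stratum effect is plausible. It also says neither showed a significant mortality effect, and SoC is chosen rather than randomised, so the documents fix neither the size nor the direction.

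**Kaplan-Meier.** Censoring a patient at death treats that patient as still able to progress later. One minus Kaplan-Meier then estimates progression in a population where nobody dies, yet it would be tabulated as the share of patients who progressed. It can never be lower than the true cumulative incidence, and it exceeds it once a progression-free death precedes a later progression in the same arm. The gap grows with mortality, so it can also distort the difference in percentages between arms.

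**Working it through.** **What the plan quantifies.** Only the FVC endpoint is powered (Protocol 11.7: 58 patients, SD 250 ml, difference 160 ml, one-sided 10%). With 29 per arm, SE = 250 × √(2/29) = 65.65 ml and power = Φ(160/65.65 − 1.2816) = 87.6%, consistent with the stated minimum of 80%. Protocol 11.8 gives no power for secondary variables, so every event rate below is an assumption.

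**1. Strata: power of the one-sided 10% log-rank test**

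Assumptions: 29 per arm, randomised 1:1 within strata; strata of 18 (neither drug), 20 and 20; control hazard −ln(0.65) per 48 weeks, i.e. 35% with the event on SoC; treatment HR 0.5; progression detected at the four quarterly visits; 15% drop-out. There were 20,000 simulated trials per cell (Monte Carlo SE about 0.35 point).

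| HR of 'neither' stratum | Unstratified % | Stratified % |
|---|---|---|
| 0.4 | 45.1 | 45.8 |
| 1 | 50.3 | 50.1 |
| 1.5 | 53.0 | 53.1 |
| 2 | 54.9 | 55.7 |
| 2.5 | 55.4 | 57.6 |
| 3 | 55.4 | 58.7 |
| 4 | 55.2 | 61.2 |

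- Strata of 6/26/26: loss at most 1.1 points up to stratum HR 3, and 2.8 points at 4.
- Null rejection, unstratified vs stratified: 10.2% vs 10.2% at stratum HR 1, 9.6% vs 10.2% at 2, 8.9% vs 10.4% at 3, 7.6% vs 10.1% at 4.
- Large-sample unstratified HR: 0.51, 0.52 and 0.54 at stratum HR 2, 3 and 4, against a true within-stratum 0.50.
- A separate simulation (strata 24/24/10 and 29/23/6, 40% placebo progression, stratum HRs 1 to 3, 6,000 runs per scenario) gave a largest gain of about 2 points (51.0% vs 53.0%).
- Mortality: at 10% control mortality (about 4 deaths) and stratum HR 1, power is 29.3% unstratified and 29.1% stratified. For control mortality of 5 to 27%, the two differ by at most 0.3 point at stratum HR 1 to 2.

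**2. Kaplan-Meier against cumulative incidence**

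Let h1 be the progression hazard and h2 = −ln(1 − mortality) the hazard of death, both per 48 weeks and constant.

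- 1 − KM = 1 − exp(−h1)
- True incidence = h1/(h1 + h2) × [1 − exp(−(h1 + h2))]

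Take h1 = 0.45 (assumed), so 1 − KM = 36.2%. Protocol 1.1 gives a median survival of 2 to 5 years from diagnosis. Then 48-week mortality = 1 − exp(−ln 2/median × 48/52.18), which is 12.0% for 5 years and 27.3% for 2 years. That is probably high for this population, so 3% and 5% are shown too.

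| Mortality | h2 | True incidence % | Gap (points) | Patients of 29 |
|---|---|---|---|---|
| 3% | 0.030 | 35.7 | 0.5 | 0.15 |
| 5% | 0.051 | 35.4 | 0.8 | 0.25 |
| 12% | 0.128 | 34.2 | 2.1 | 0.6 |
| 27% | 0.315 | 31.5 | 4.8 | 1.4 |

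- With quarterly detection and the SAP censoring rule, true incidence is 33.6% at 12% mortality and 30.2% at 27%, gaps of 2.6 and 6.0 points.
- Over 20 to 50% progression and 3 to 20% mortality, the quarterly version gives 0.4 to 5.9 points.
- For IPF-related mortality, PFS2 and composite (b), with 1 to 5% non-IPF deaths, the gap is 0.05 to 1.2 points.
- For scale, the 80% CI half-width at 36% and n = 29 is 1.2816 × √(0.36 × 0.64/29) = 0.114, about 11 points.

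**The case against.** The unstratified log-rank is a valid pre-specified test, the protocol and SAP agree on it, and it does not inflate type I error. The trial is declared exploratory and these endpoints are unpowered. The 6-point power loss needs a stratum HR of 4 with 18 of 58 patients (31%) on neither drug; at moderate effects nothing is lost, and for mortality stratifying gains almost nothing. A redacted block sits directly above the SAP paragraph and might hold a rule.

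On Kaplan-Meier, the excess is zero if no one dies. SAP 6.2.2 already plans a list and summary of progression events, and PFS1 and composite (a) count death as an event. Inclusion criterion 8 makes non-IPF deaths unlikely.

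Most of this stands, and it is why the point is minor. Three parts do not remove it:

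- The log-rank and Cox sentences are complete as printed. In 6.2.3.2 the SAP describes treatment in the same terms and then adds SoC explicitly, so its absence from 6.2.3.1 reads as an omission. A hidden rule cannot be excluded, but the protocol names no strata either.
- The event summary shows how many patients were seen to progress but does not correct the tabulated percentage, and a crude count makes no allowance for drop-out.
- DLCO and 6MWD progression have no individual version that counts death. Wide intervals do not justify a wrong label.

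**Conclusion.** Both parts hold, and both are minor.

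**Strata.** The time-to-event tests depart from the randomisation scheme and from the rest of the SAP. Under the assumed rates the cost is about 0 to 1 point of power up to a stratum HR of 2, 2 to 3 points at 2.5 to 3, and 6 points only at 4 with a large untreated stratum. The test errs towards conservatism.

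**Kaplan-Meier.** The direction of the error follows from the censoring rule; only its size is assumed. It is below 1 point at 3 to 5% mortality and 2 to 6 points at 12 to 27%, always less than the 11-point half-width. It affects the three disease-progression endpoints and, much less, IPF-related mortality, PFS2 and composite (b). All-cause mortality, PFS1 and composite (a) are unaffected. The log-rank and Cox results remain valid as cause-specific comparisons. The primary FVC analysis is not touched.

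**What to change.** In SAP 6.2.3.1:

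1. Specify a log-rank test stratified by SoC and a Cox model with SoC as a stratification variable. Keep the unstratified versions as a check, especially for mortality, where events are few.
2. For the three disease-progression endpoints, report Aalen-Johansen cumulative incidence with death as the competing event.
3. Do the same for IPF-related mortality, PFS2 and composite (b), with non-IPF death as the competing event.
4. Describe the hazard ratios for those endpoints as cause-specific. Leave all-cause mortality, PFS1 and composite (a) on Kaplan-Meier.

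The cost is SAP wording and standard procedure options, with no new data. The downside is up to about 0.3 point of power if SoC turns out not to be prognostic, and sparse strata will contribute little to the mortality tests.
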